3.3.4 Removal of patients from therapy or assessments

3.3.4.1 Removal of individual patients

Removal of individual patients from therapy:

An individual patient is to be withdrawn from trial treatment if:

- The patient withdraws consent for study treatment or study participation, without the need to justify the decision.
- The patient needs to take concomitant drugs that interfere with the investigational product or other trial medication (see [section 4.2.2](#)).
- Patient becomes pregnant during the trial. Patient will be followed up until birth or otherwise termination of the pregnancy.
- The patient is no longer able to participate for other medical reasons (e.g. surgery, AEs, or other diseases or finding of the medical examination including safety laboratory tests, vital signs and ECG) based on the opinion of the investigator.
- The patient develops an anaphylactic reaction (cf. [section 4.2.1](#) and [5.3.5.1](#)).
- In case of worsening or flare at any time point, the investigator may allow patients to discontinue and start rescue therapy according to the available guidelines for treatment of LN

In case a patient withdraws drug prematurely, it is important that his/her renal function parameters and safety data are recorded until the end of the 52 weeks period. Thus, all patients will be asked to follow some visits until 52 weeks. The patient will undergo the procedures for early treatment discontinuation and continue visits as described in [section 6.2.3](#) until week 52.

For all patients the reason for withdrawal (e.g. adverse events) must be recorded in the (e)CRF. These data will be included in the trial database and reported.

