4.2 CONCOMITANT THERAPY, RESTRICTIONS, AND RESCUE TREATMENT

4.2.1 Rescue medication, emergency procedures, and additional treatment(s)

There are no special emergency procedures to be followed.

Background medication:

All patients will receive standard of care (SOC) treatment for lupus nephritis based on MMF:

SOC Initial phase (week 1 – 26):

- MMF: patients who are already on MMF of 2 g/day or a maximum of 3 g/day should stay at same MMF dose, provided that they have tolerated it well. Patients who start treatment with MMF or patients with a dose <2g/day should be increased to a stable MMF dose of 2g/day. It is recommended not to increase MMF above 2g/day to reduce the risk of severe side-effects of MMF. In case of side effects related to MMF, a MMF dose < 2g/day is allowed.
- AND glucocorticosteroids (GC) (methylprednisolone, recommended 500mg pulse IV for 3 days) followed by oral glucocorticosteroids, tapering to 10mg prednisone equivalent/day within 12 weeks. Tapering of steroids should follow the tapering schedule in [Appendix 10.1](#). Patients who have had already a course of IV steroids (up to a total dose of maximum 3g if it had been considered necessary by the investigator) within 6 weeks prior to randomization should not necessarily repeat it depending on what they received. They should only have necessary pulses to reach a total of 1.5g IV steroids. E.g : if they have already received 2 pulses of 500mg, they will just receive one additional pulse. If they have already had 3 *500 mg, they simply do not repeat any IV pulse. If considered necessary by the investigator, a maximal dose of 1000 mg methylprednisolone per day for up to 3 days (maximal 3000mg) is acceptable.

SOC week 26 – 52:

- Mycophenolate mofetil (MMF) 1 to 2 g/day stable + low-dose (≤ 10 mg/day) prednisone-equivalent

From week 26 only, in case of side effects: MMF may be reduced to 1g/day or in case of non tolerability, patients could be switched to Azathioprine (AZA) 2mg/kg/day + (≤ 10 mg/day) prednisone-equivalent low-dose daily.

In patients who experience a worsening or a flare, the investigator is allowed to increase the steroid dose for the patient. These patients are allowed to continue treatment with BI 655064 until week 52..

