4.2.2 Restrictions

4.2.2.1 Restrictions regarding concomitant treatment

Concomitant medications (or therapy) to provide adequate care may be given as clinically necessary. If a restricted concomitant therapy is necessary, treatment with study medication should be permanently discontinued

The [Table 4.2.2.1: 1](#) specifies periods before randomization and for the whole duration of the study including the Follow-up, when specific drugs are allowed or restricted.

Table 4.2.2.1: 1 Permitted and Restricted medications

Therapy	Prior to Study	Screening Period	Randomized Treatment Period		Follow up Period
			SOC Initial phase week 0-26	SOC week 26-52	
Azathioprine	Permitted on maintenance therapy	Permitted on maintenance therapy	Not permitted	Permitted if MMF not tolerated or not authorised	Permitted
Cyclophosphamide	Not permitted (6 m prior to randomisation)	Not permitted	Not permitted	Not permitted	Not Permitted
MMF	Permitted if dose ≤ 2 g/day; doses ≤ 3 g/day permitted within 6 weeks prior randomisation	Permitted within 6 weeks prior randomisation	Permitted max 3g/day	Permitted Max 2g/day	Permitted
Cyclosporine - Tacrolimus	Not permitted 4 weeks before randomisation	Not permitted	Not permitted	Not permitted	Permitted if needed based on inv decision
Treatment with any biologic B-cell depleting therapy (e.g. anti-CD20,antiCD22) or abatacept*	Not permitted (12 m prior to visit 2)	Not permitted	Not permitted	Not permitted	Not permitted
Belimumab, antiBLyS	Not Permitted (3 months or 5 half-lives whichever is longer when used for non renal SLE, 12 months when used for renal SLE)	Not permitted	Not permitted	Not permitted	Not permitted
Investigational Medication	Not permitted (6m or 5 half-lives prior to visit 2)	Not permitted	Not permitted	Not permitted	Not permitted
IV glucocorticoids	Allow 3 g IV total max within 6 weeks prior randomisation; a single pulse should not be >1000 mg		Permitted as part of the trial regimen, according to the protocol	Not permitted	Permitted

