Description of change		Sentence moved to section 4.2.1: In patients who experience a worsening or a flare, the investigator is allowed to increase the steroid dose for the patient. These patients are allowed to continue treatment with BI 655064 until week 52
Rationale for change		Clarity
Section to be changed		4.1.5 & 7.4
Description of change		Rewording of “logistic plan” into “interim analysis trial statistical plan”
Rationale for change		Matching with the title of the referred document
Section to be changed		4.2.1
Description of change		Addition of sentence: In patients who experience a worsening or a flare, the investigator is allowed to

		increase the steroid dose for the patient. These patients are allowed to continue treatment with BI 655064 until week 52
Rationale for change		Clarify the use of glucocorticosteroids
Section to be changed		4.2.1
Description of change		Sentence deleted: "For the primary analysis, these patients will be looked upon as failures"
Rationale for change		The protocol allows some flexibility for the use of glucocorticosteroids, in no place addition of glucocorticosteroids to the recommended dose would lead to discontinuation. This drug can be administered for other reason than treatment of lupus nephritis. Therefore for patient's safety, consistencies, and to avoid misunderstandings, the sentence is deleted.
Section to be changed		4.2.1
Description of change		Sentence deleted: " In case of worsening or flare at any timepoint, the investigator may allow patients to escape to rescue therapy according to the available guidelines for treatment of LN."
Rationale for change		Delete as mentioned in 3.3.4.1
Section to be changed		4.2.1
Description of change		Addition of Azathioprine when mention done on MMF.
Rationale for change		Clarification
Section to be changed		4.3
Description of change		Addition of the sentence: "The last two intakes dates and time of MMF taken before the blood sampling will be recorded in RDC, based on patient's interview."
Rationale for change		
Section to be changed		5.2
Description of change		Deletion of the sentence: "Patients who did not reach 10 mg prednisone-equivalent within 12 weeks or needed an increase in steroid dose above 10 mg after the 12 weeks, will be considered as Non- Responder for the primary analysis"

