D1	Prohibited medication use	
 • Azathioprine during weeks 0-26 • Cyclophosphamide 6 months prior to randomization through Week 52 • Cyclosporine-Tacrolimus during 4 weeks prior to randomization through Week 52 • Any biologic B-cell depleting therapy (e.g. anti-CD20, anti-CD22) or Abatacept during 12 months prior to randomization through Week 52 • anti-Blyss 3 months prior to randomization for non renal SLE or 12 months for renal SLE through Week 52 • Investigational medication for 6 months or 5 half lives prior to randomization through week 52 • IV glucocorticoids during Week 40-52. (Manual iPDs)	PPS/ (TBD at MQRM/ BRPM)
D2	Non-permitted oral steroid use	Patient used more than 10 mg per day of oral steroid at any time during the interval from week 40 to week 52.	PPS/ (TBD at MQRM/ BRPM)
D3	Non-permitted MMF dose	MMF >3g per day up to week 26 or average MMF >2.5 g per day after week 26	PPS/ (TBD at MQRM/ BRPM)
G	Trial specific		
G1	Failure to remove patient from therapy	As described in CTP section 3.3.4.	PPS/ (TBD at MQRM/ BRPM)
Z	Other		
Z1	Other iPDs affecting efficacy and possibly safety		PPS/ (TBD at MQRM/ BRPM)
Z2	Other iPDs affecting safety only		None

*The numbering of exclusion criteria changed with one or more of the protocol amendments. The numbering, reflected in the data sets and in later eCRFs, is shown in brackets.

Proprietary confidential information © 2020 Boehringer Ingelheim International GmbH or one or more of its affiliated companies

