7.4 PRIMARY ENDPOINT

7.4.1 Primary analysis of the primary endpoint

Primary analyses of the primary endpoint will be performed using the ITT patient set.

The Multiple Comparison Procedures and Modeling (MCP-Mod) approach (4, 5) is implemented in two main steps: (1) trial design stage; (2) trial analysis stage. The procedures for the trial design stage, including the selection of candidate models covering a suitable range of dose-response shapes and sample size and power calculations, are provided in the CTP Section 7.3.1 and 7.7. The procedures for the trial analysis stage are outlined below with more specification (including SAS code & R code) in [Section 9.1](#).

CRR at week 52 (derived using UP and derived using UP/UC from the 24h urine collections) will be analysed using a logistic regression model. Factors in the model will include treatment and the covariates: race (Asian/non-Asian) and proteinuria at screening $<3\text{g/day}$ or $\geq 3\text{g/day}$ (respectively $U_{\text{prot}}/U_{\text{creat}} < 3$ or $U_{\text{prot}}/U_{\text{creat}} \geq 3$). Use of proteinuria at screening as a covariate was not specified in the CTP. It was added via the TSAP as both race and proteinuria were stratification variables at randomization.

From this model, placebo-adjusted treatment estimates for each active dose group, as well as their corresponding variance-covariance matrix will be estimated. These results will be used in the MCPmod analysis.

Pairwise comparisons of the *modelled proportion* of patients at each dose level who are CRRs will be compared to placebo. In keeping with the exploratory nature of the trial, p-values will be interpreted in a nominal fashion (no adjustment for multiplicity will be performed). While the interim TSAP specified that an alpha level of 0.10 (two-sided) would be the cut-off for declaring statistical significance, this was changed via the Decision log prior to conducting the interim analysis. For consistency with a team-reviewed relevant external publication it was decided that an alpha level of < 0.20 (two-sided) would be the cut-off for declaring statistical significance.

Pairwise comparisons of the *observed* proportions of patients at each dose level to placebo who are CRRs will be performed. Confidence intervals will be calculated using the Newcombe method. P-values from Barnard tests of association will be displayed.

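### For a flare treated with IV glucocorticoid after week 26, the protocol supports both continuing and stopping study drug, and that choice can decide the patient's primary outcome

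*Protocol*

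**What the plan says.** **Protocol 4.2.1**, directly after the week 26-52 background regimen: "In patients who experience a worsening or a flare, the investigator is allowed to increase the steroid dose for the patient". The next sentence reads: "These patients are allowed to continue treatment with BI 655064 until week 52". Neither sentence gives a route, a dose limit or a period.

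**Protocol 4.2.2.1**: "If a restricted concomitant therapy is necessary, treatment with study medication should be permanently discontinued". In Table 4.2.2.1: 1 the IV glucocorticoid row reads "Permitted as part of the trial regimen, according to the protocol" for weeks 0-26. The next cell, for weeks 26-52, is marked as not permitted.

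**Protocol 3.3.4.1** calls for withdrawal from treatment when a patient needs interfering concomitant drugs, and refers to 4.2.2. It also says: "In case of worsening or flare at any time point, the investigator may allow patients to discontinue and start rescue therapy".

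**SAP 7.4.1**: "Primary analyses of the primary endpoint will be performed using the ITT patient set".

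**SAP 6.6.1** has four ITT rules for patients who stop trial medication early. Rule 1 makes a stop for lack of efficacy or worsening of the disease a non-response. Rule 2 does the same for prohibited medication that affects CRR, but only when it is used after study drug has been stopped. Rule 3 uses week-52 laboratory data if treatment lasted at least 46 weeks. Rule 4 makes any other stop before 46 weeks a non-response.

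**SAP Table 6.2: 1**, deviation D1, includes "IV glucocorticoids during Week 40-52". D2 covers oral steroid above 10 mg/day in the same weeks. Both bear on the per-protocol set (PPS), subject to later review, and not on the ITT set.

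**The concern.** For an IV pulse given for a flare after week 26, 4.2.1 can be read to allow continued study drug, while 4.2.2.1 says study drug should be stopped. Section 3.3.4.1 does not settle it: one bullet points to 4.2.2 for withdrawal, and another leaves discontinuation at a flare to the investigator.

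The choice matters because stopping study drug is itself an outcome in the primary analysis. Two patients with the same flare, the same pulse and the same week-52 laboratory values can be scored differently because their sites relied on different sections. The protocol plans 1-2 patients per site across roughly 80 to 100 sites, so consistent practice has to come from the text. If flares are equally common in all arms, the result is mainly noise and a shift in level. If they are more common on placebo, which is plausible if the drug works, the rule applied also changes the contrast between arms.

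**Working it through.** **1. Trace one patient through the SAP.** Take a flare at week 30 treated with an IV pulse.
- *Site applies 4.2.2.1.* Study drug stops at about week 30. That is under 46 weeks, so the patient is a non-responder by rule 4, or by rule 1 if the reason recorded is lack of efficacy or worsening of the disease.
- *Site applies 4.2.1.* Study drug continues. The early-stopping rules do not apply, and rule 2 would not reach this use in any case because it concerns use after stopping. The visible SAP has no other ITT rule for added steroid on treatment. The week-52 laboratory values decide, and CRR is possible.

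The split is cleanest for a stop before week 46. After that, rules 1 and 2 or the week-52 data apply.

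**2. Size per patient, observed rates.** Planned arms are 40 placebo, 20 at 120 mg, 20 at 180 mg and 40 at 240 mg.
- 1/20 = 5 points
- 1/40 = 2.5 points

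**3. Size per patient, modelled benefit.** Protocol 7.3.1 applies the 10-point target-dose criterion to the modelled curve. I refitted logit-scale curves to the Expected A rates (0.25, 0.30, 0.38, 0.44). Shape parameters are assumed because the candidate-shape figure is not shown: Emax with ED50 60, exponential with delta 100, quadratic peaking at 200, sigmoid Emax with ED50 150 and h = 4, and a linear curve.
- Two extra responders at 120 or 180 mg change the maximum modelled benefit by about -2 to +3 points.
- Four extra responders on placebo or at 240 mg change it by about 6 to 10 points in absolute size.

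**4. Plan's own figure.** Expected A is stated at 82% success. A simulation of 20,000 runs with a four-shape maximum-contrast test (the shapes in step 3 without the linear curve), one-sided 20%, plus a modelled benefit of at least 10 points, gives 83.4%. The design figure reproduces.

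**5. Illustration across a trial.** The documents give no rate of IV use after week 26. Assume that 5-15% of placebo patients are pulsed between weeks 26 and 46, and that 25-75% of those would meet the CRR laboratory criteria if kept on drug. The planned rates are taken as the case where every such patient stops. If every such patient continues, each arm gains (share pulsed) x (share meeting criteria).
- *Equal shares in all arms.* The gain runs from 0.05 x 0.25 = 1.25 points to 0.15 x 0.75 = 11.25 points. The 240 mg difference stays at 0.44 - 0.25 = 19 points, and success stays at about 81-83%.
- *Half the share on active drug, smallest case.* Placebo 0.25 + 0.05 x 0.25 = 0.2625; 240 mg 0.44 + 0.025 x 0.25 = 0.44625; difference 18.4 points; success about 81%.
- *Half the share on active drug, largest case.* Placebo 0.25 + 0.15 x 0.75 = 0.3625; 240 mg 0.44 + 0.075 x 0.75 = 0.49625; difference 13.4 points; success about 64%.

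These compare all sites stopping with all sites continuing. Mixed practice with the same mix in every arm lies between.

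**6. Deviation window.** The table bars IV glucocorticoids in weeks 26-52, while D1 lists weeks 40-52. Weeks 26-39, about 14 weeks, are barred but not named in D1.

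**The case against.** The strongest reply is that the passages have an ordinary reading together. The flare sentence follows a regimen stated as a daily prednisone-equivalent dose, so an increase most naturally means that dose. The table restricts one route, and a specific restriction normally limits a general permission. This is plausible and would remove the conflict, but 4.2.1 does not say it, and the same section uses its steroid wording for both IV pulses and oral dosing. The Amendment 6 rationale, "in no place addition of glucocorticosteroids to the recommended dose would lead to discontinuation", points away from a mandatory stop. It is weak support, though: it explains a deleted sentence, does not mention IV use and does not instruct sites.

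Other parts of the reply stand:
- The wording in 4.2.2.1 is that study medication should be discontinued, which is softer than an absolute requirement.
- Section 3.3.4.1 gives the investigator discretion at a flare, so some dependence on the site would remain after any clarification.
- A reader might infer that an IV pulse in weeks 26-39 goes unnoticed in the PPS. The documents do not support that. Deviation G1 covers failure to remove a patient under protocol 3.3.4, which refers to 4.2.2. Z1 is a catch-all, and the SAP calls the list a working one.
- A reader might infer that D1 must match the period of prohibition. It need not. D1 defines deviations for analysis and is not a rule for sites. Its window matches D2, and SAP section 4 declares that the deviations were updated on expert advice, so the choice may be deliberate.
- SAP 7.4.2 shows no text, so a relevant sensitivity analysis cannot be ruled out.

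**Conclusion.** The point holds for IV glucocorticoids given for a flare after week 26. Current protocol text can be cited for continuing and for stopping study drug, and for a stop before week 46 the choice carries into the ITT primary endpoint. An oral increase is not a restricted item in the table as shown, so the conflict does not extend to it.

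Each affected patient moves the observed rate by 5 or 2.5 points, depending on the arm. It is tempting to read 10 points as two patients in a 20-patient arm. That does not follow, because the criterion is on modelled efficacy, where two such patients shift the benefit by only about -2 to +3 points under the assumed shapes.

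The overall effect cannot be established from the documents. In the illustration, success is nearly unchanged when IV use is equal across arms. It falls materially only when use differs by arm and many pulsed patients would meet the CRR criteria. The case for change is that the ambiguity is avoidable and reaches the primary outcome, not that a given loss of power has been shown.

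**What to change.** Reconcile protocol 3.3.4.1, 4.2.1 and 4.2.2.1 with its table, so that one rule states, by route and period, which steroid increases allow continued study drug and which do not. Which rule is clinically right is for the sponsor and investigators to decide, and this review takes no position on it.

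Then check the IV glucocorticoid window in SAP deviation D1 against the reconciled rule. Either align it, or state that weeks 26-39 are left out on purpose and whether G1 applies to IV use in those weeks.

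The cost is one protocol clarification, a line or two in the SAP and possibly a slightly smaller PPS. Investigator discretion at a flare under 3.3.4.1 may still leave some variation between sites.

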4.2.2 Restrictions

4.2.2.1 Restrictions regarding concomitant treatment

Concomitant medications (or therapy) to provide adequate care may be given as clinically necessary. If a restricted concomitant therapy is necessary, treatment with study medication should be permanently discontinued

The [Table 4.2.2.1: 1](#) specifies periods before randomization and for the whole duration of the study including the Follow-up, when specific drugs are allowed or restricted.

Table 4.2.2.1: 1 Permitted and Restricted medications

Therapy	Prior to Study	Screening Period	Randomized Treatment Period		Follow up Period
			SOC Initial phase week 0-26	SOC week 26-52	
Azathioprine	Permitted on maintenance therapy	Permitted on maintenance therapy	Not permitted	Permitted if MMF not tolerated or not authorised	Permitted
Cyclophosphamide	Not permitted (6 m prior to randomisation)	Not permitted	Not permitted	Not permitted	Not Permitted
MMF	Permitted if dose ≤ 2 g/day; doses ≤ 3 g/day permitted within 6 weeks prior randomisation	Permitted within 6 weeks prior randomisation	Permitted max 3g/day	Permitted Max 2g/day	Permitted
Cyclosporine - Tacrolimus	Not permitted 4 weeks before randomisation	Not permitted	Not permitted	Not permitted	Permitted if needed based on inv decision
Treatment with any biologic B-cell depleting therapy (e.g. anti-CD20,antiCD22) or abatacept*	Not permitted (12 m prior to visit 2)	Not permitted	Not permitted	Not permitted	Not permitted
Belimumab, antiBLyS	Not Permitted (3 months or 5 half-lives whichever is longer when used for non renal SLE, 12 months when used for renal SLE)	Not permitted	Not permitted	Not permitted	Not permitted
Investigational Medication	Not permitted (6m or 5 half-lives prior to visit 2)	Not permitted	Not permitted	Not permitted	Not permitted
IV glucocorticoids	Allow 3 g IV total max within 6 weeks prior randomisation; a single pulse should not be >1000 mg		Permitted as part of the trial regimen, according to the protocol	Not permitted	Permitted

4.2.2.2 Restrictions on diet and life style

Patients should not donate blood during MMF therapy and for at least 6 weeks following discontinuation of MMF.

Men should not donate semen during MMF therapy and for at least 90 days following discontinuation of MMF

During the trial, all patients should avoid intensive physical activity and unprotected exposure to direct sunlight. The use of tanning booths is forbidden. Intensive physical activity is considered activity that is of a higher intensity than usually performed by the individual. Fasting is not required for this study.

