3.3.2 Inclusion criteria

1. Male or female patients. Women of childbearing potential* must be ready and able (as assessed by investigator) to use simultaneously two reliable methods of birth control, one of which must be highly effective. Highly effective method, per ICH M3(R2) is a method that result in a low failure rate of less than 1% per year when used consistently and correctly. The reliable contraception should be used before starting MMF therapy and the study drug, during the treatment and until 50 days after stopping MMF and the study drug.
A list of contraception methods meeting these criteria is provided in the patient information.
Sexually active men must be ready to use condoms^s during treatment with MMF and for at least 90 days after cessation of MMF treatment.
2. Age 18 –70 (inclusive) years at visit 1; For patients in Japan age 20-70 is applicable at visit 1
3. Diagnosis of systemic lupus erythematosus (SLE) by ACR criteria 1997, at least 4 criteria must be documented, one of which must be a positive anti-dsDNA antibody OR a positive antinuclear antibody (ANA) at screening or around time of start of induction therapy.

4. Lupus Nephritis Class III or IV (ISN/RPS 2003 classification) with either **active or active/chronic** disease, co-existing class V permitted, proven by renal biopsy within 3 months prior to screening or during screening in case induction therapy for LN has not yet been started
5. Active renal disease evidenced by proteinuria ≥ 1.0 g/day [(Uprot/Ucrea) ≥ 1] at screening
6. Signed and dated written informed consent must be obtained from each patient prior to participation to the trial in accordance with GCP and local legislation

*Women of childbearing potential are defined as:

Any female who has experienced menarche and does not meet the criteria for "women not of childbearing potential" as described below.

Women not of childbearing potential are defined as:

Women who are postmenopausal (12 months with no menses without an alternative medical cause) or who are permanently sterilized (e.g. hysterectomy, bilateral oophorectomy or bilateral salpingectomy).

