\$ Condom use applies for both reproductively competent and vasectomized men, because the risks associated with the transfer of seminal fluid also apply to men who have had a vasectomy. In addition, female partners of male patients treated with MMF/AZA are recommended to use highly effective contraception during treatment and for a total of 90 days after the last dose of MMF/AZA.

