- Changes in vital signs, ECG, physical examination and laboratory test results, if they are judged clinically relevant by the Investigator.

If such abnormalities already pre-exist prior trial inclusion they will be considered as baseline conditions.

All (S)AEs, including those persisting after trial completion must be followed up until they have resolved, have been sufficiently characterized, or no further information can be obtained.

SAEs which occurred during the screening period are to be reported according to standard procedures.

Pregnancy

Due to the teratogenic potential of MMF/AZA, highly effective contraception has to be performed. The reliable contraception should be used in female patient before starting MMF therapy and the study drug, during the treatment and until 50 days after stopping MMF and the study drug (and until 90 days after stopping AZA in case of AZA is used).

A list of contraception methods meeting these criteria is provided in the patient information. Sexually active men must be ready to use condoms^s during treatment with MMF/AZA and for at least 90 days after cessation of MMF/AZA treatment.

In the rare case that a female subject participating in this clinical trial becomes pregnant after having taken trial medication, the Investigator must report immediately (within 24 hours) the drug exposure during pregnancy (DEDP) to the Sponsor's unique entry point (country-specific contact details will be provided in the ISF). The Pregnancy Monitoring Form for Clinical Trials (Part A) should be used.

The outcome of the pregnancy associated with the drug exposure during pregnancy must be followed up and reported to the Sponsor's unique entry point on the Pregnancy Monitoring Form for Clinical Trials (Part B).

As pregnancy itself is not to be reported as an AE, in the absence of an accompanying SAE, only the Pregnancy Monitoring Form for Clinical Trials and not the SAE form is to be completed. If there is an SAE associated with the pregnancy then the SAE has to be reported on the SAE form in addition.

Similarly, potential drug exposure during pregnancy must be reported if a partner of a male trial participant becomes pregnant. This requires a written consent of the pregnant partner.

The ISF will contain the Pregnancy Monitoring Form for Clinical Trials (Part A and B), as well as information and consent form for the pregnant partner.

.

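### The semen-donation limit in protocol section 4.2.2.2 follows MMF only, so for a man switched to azathioprine it can end while he is still taking a drug the protocol calls teratogenic

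*Protocol*

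**What the plan says.** - **Donation.** Section 4.2.2.2 is the only place that governs donation. For semen it says: "Men should not donate semen during MMF therapy and for at least 90 days following discontinuation of MMF". The blood-donation sentence beside it also names MMF only, with 6 weeks instead of 90 days.
- **Switching.** From week 26, section 4.2.1 provides that, if MMF is not tolerated, "patients could be switched to Azathioprine (AZA) 2mg/kg/day". Table 4.2.2.1:1 lists AZA for weeks 26-52 as "Permitted if MMF not tolerated or not authorised", and it also permits AZA in follow-up.
- **Contraception during the trial.** The Pregnancy part of section 5.3.6 refers to the "teratogenic potential of MMF/AZA". It requires sexually active men to use condoms "during treatment with MMF/AZA and for at least 90 days after cessation of MMF/AZA treatment".
- **Footnote to inclusion criterion 1 (section 3.3.2).** Condom use extends to vasectomised men because of "the risks associated with the transfer of seminal fluid". Female partners are "recommended to use highly effective contraception during treatment and for a total of 90 days after the last dose of MMF/AZA".
- **Inclusion criterion 1 itself.** The condom sentence reads "during treatment with MMF and for at least 90 days after cessation of MMF treatment", without AZA. For women, the rule ends 50 days after MMF and study drug. It lacks the 90-day extension after AZA that section 5.3.6 gives.

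**The concern.** The change from MMF to AZA is a planned treatment path. For reproductive risk the protocol treats the two drugs alike in section 5.3.6 and in the partner advice of the criterion 1 footnote: same hazard, same 90 days. The semen-donation rule does not follow. Its clock starts when MMF stops and takes no account of AZA.

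A man who switches is therefore still bound by the condom rule, but the donation rule can expire during AZA treatment. Donation is itself a transfer of seminal fluid, which is the route the protocol gives as its reason for condom use. Any harm would fall on people outside the trial, whom the condom rule does not protect. No estimate or test in the trial depends on this; it is a safety instruction that contradicts the reasoning given elsewhere in the same protocol.

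**Working it through.** The plan states no figure to reproduce. The check compares the rules and then applies day arithmetic to the visit schedule.

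**Rules side by side**

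| Rule | Drug named | Ends |
|---|---|---|
| Semen donation, 4.2.2.2 | MMF | 90 days after MMF (minimum) |
| Condoms, 5.3.6 | MMF/AZA | 90 days after MMF/AZA (minimum) |
| Partner contraception, criterion 1 footnote | MMF/AZA | 90 days after last dose |
| Condoms, criterion 1 | MMF | 90 days after MMF (minimum) |

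**Inputs**

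- Flow Chart days: week 26 = Day 183 (visit 11), week 30 = Day 211 (visit 12), week 35 = Day 246 (visit 13), week 52 = Day 365, end of study = Day 421.
- Washout: 90 days in each rule.
- Assumption: MMF stops on the switch day *t*, and AZA then runs to Day 365.

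**Formulas**

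- End of donation limit = *t* + 90.
- Days on AZA with no donation limit = 365 − (*t* + 90), or 0 if negative.
- End of condom period = 365 + 90 = Day 455.
- Shortfall against the condom period = 455 − (*t* + 90) = 365 − *t*, which is the time spent on AZA.

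**Results**

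| Switch day *t* | Donation limit ends | Days on AZA without limit | Shortfall to Day 455 |
|---|---|---|---|
| 183 | 183 + 90 = 273 | 365 − 273 = 92 | 455 − 273 = 182 |
| 211 | 211 + 90 = 301 | 365 − 301 = 64 | 455 − 301 = 154 |
| 246 | 246 + 90 = 336 | 365 − 336 = 29 | 455 − 336 = 119 |
| 275 | 275 + 90 = 365 | 365 − 365 = 0 | 455 − 365 = 90 |

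A switch before Day 275 lets the limit lapse while AZA continues. From Day 275 there is no gap before week 52, but the limit still ends earlier than the condom period.

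The stop at Day 365 is not the longest case, because AZA is also permitted in follow-up. If AZA ran to Day 421 after a switch at Day 183, the man would have 421 − 273 = 148 days on AZA without the limit. The shortfall against the condom period would be 421 − 183 = 238 days.

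**Does another rule close the gap?** No. The condom rule applies to sexual activity and does not govern donation, and no other section extends the donation limit to AZA.

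**The case against.** The best counter-argument is about the source of the rule. The amendment history shows that both donation limits came in with global amendment 2, to reflect the updated MMF product information. Nothing in the documents says that AZA labelling carries a donation limit, and section 5.3.6 never mentions donation. On this view, going from condoms on AZA to no donation on AZA is an inference, and the semen sentence deserves no firmer treatment than the blood sentence.

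This does not remove the point. The protocol itself assigns teratogenic potential to AZA and requires 90 days of protection after it for male patients. No outside label is needed to see that a donation limit ending during AZA conflicts with that. Blood donation is different, because no part of the documents links AZA to it; that half of the objection stands and is a question for the sponsor's medical team.

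Other parts also stand:

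- Section 4.2.2.2 is silent on AZA rather than giving express permission, and 90 days is a minimum.
- The group is small: men, among 120 randomised patients, who leave MMF for AZA after week 26 and wish to donate.
- The shortfall figures equal the assumed time on AZA, so they measure duration and not the number of people affected.
- The patient information is not among the documents and may already cover this.
- The mismatch in criterion 1 is wording only. That criterion governs entry, and section 5.3.6 already sets the AZA rule for both sexes.

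**Conclusion.** The concern holds. As written, section 4.2.2.2 can release a man from the semen-donation limit while he takes AZA, against the protocol's own reasoning in section 5.3.6 and the criterion 1 footnote. With AZA to Day 365, the unprotected time on AZA is 92 days for a switch at Day 183 and falls to 0 for a switch at Day 275. The limit ends 182 to 90 days before the condom period over the same range. Release is never immediate, because the 90-day MMF washout still runs after the switch.

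The arithmetic rests on MMF stopping on the day of the switch and on the assumed AZA stop day. The number of men affected cannot be estimated from the documents. Contraception does not lapse: section 5.3.6 covers AZA for both sexes, and the women's entry rule also runs on study drug. The most likely origin is an incomplete update: amendment 6 added AZA beside MMF in section 4.2.1 and brought the MMF/AZA contraception text into section 5.3.6, while 4.2.2.2 still names MMF alone. The sentence should be corrected, though the small group limits the urgency.

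**What to change.** 1. In section 4.2.2.2, replace MMF with MMF/AZA at both places in the semen sentence, so that the 90 days count from the last of the two drugs.
2. In inclusion criterion 1, write MMF/AZA in the condom sentence. For women, add the extension to 90 days after stopping AZA, where AZA is used, to match section 5.3.6. This is tidying only.
3. Carry the change into the patient information if it is not already there.
4. Ask the sponsor's medical team whether the blood-donation limit should also cover AZA. The documents give no basis for deciding it either way.

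The cost is amendment wording and, if needed, patient-information text. No patients, visits or analyses are added.
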